5.10 Criteria for evaluation of trial objectives and safety

5.10.1 Description of subject groups for analysis

Safety analysis population

Patients will be included in the safety analysis if they receive at least one dose of study treatment.

ITT analysis population

Patients will be included in the ITT analysis if they have been diagnosed with cholera due to *V. cholerae* O1 or O139 and have received at least one dose of study treatment. Patients regarded as treatment failures, as discussed above, will be included in the ITT analysis.

PP analysis population

Patients will be included in the PP analysis if they satisfy the criteria for a valid course. Patients regarded as treatment failures (continuation of watery stool for > 48 hours) will be included in the PP analysis.

Definition of a valid course

For a course of therapy to be valid for evaluating the efficacy of treatment, the following criteria must be met and documented in the CRF:

- *V. cholerae* O1 or O139 must have been isolated from either the stool or rectal swab culture performed before initiation of the study drug on the day of admission (pre-therapy).
- No other systemic antimicrobial agent must have been administered concomitantly with the study drug unless it is done consequent to declaration of “clinical failure”.
- Documented adequate compliance with administration of the single ciprofloxacin dose, or at least 10 doses of the erythromycin medication. Non-compliance will also be considered if two consecutive doses of the study medication are missed by a patient.
- No protocol violations influencing the treatment efficacy.
- The patient must have met the inclusion/exclusion criteria.
- Efficacy data from the test of cure visit is available, unless there has been an earlier treatment failure.

Pharmacokinetic population

Ciprofloxacin concentrations will be determined in the first 20 patients aged 2-5 years, and in the first 20 patients aged > 5 years who enter the study. Ciprofloxacin concentrations will also be determined in all patients who vomit within 30 minutes of receiving their first dose of medication.

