5.9 Removal of subjects from trial

It is the responsibility of the investigator to maintain the patients in the study. However, a patient may be withdrawn prematurely from the study for any of the reasons mentioned below. The reasons must be documented in the CRFs:

- Lack of clinical efficacy:
In the event no response to treatment (significant remission of clinical signs and symptoms) is observed, or if the clinical condition of the patient deteriorates within 48 hours of initiation of the study drugs, the study drug will be stopped and such patients will be treated with an effective alternative drug as described under Section 5.6.1, Reporting treatment failures.
- Significant adverse events and clinical deterioration:
In the event of a significant adverse event or deterioration in the clinical condition which would preclude further participation in the study, for example:
 - Serious toxic or allergic reaction.
 - Intercurrent diseases.
 - Aggravation of a concomitant disease.
 - Serious laboratory abnormality.
- Withdrawal of consent.
- Protocol violations.
- If the child vomits within 30 minutes of administration of study drug, any other treatment may be given and the patient will be withdrawn from the trial.

Procedures at premature termination of treatment

If a patient's clinical condition shows no sign of improvement or deteriorates 48 hours after initiation of the study drug, or if a patient develops a serious adverse event or allergic reaction, or if a superinfection develops, or if both the admission stool and rectal swab culture fail to grow *V. cholerae*, the study drug will be stopped and appropriate management will be instituted. However, before institution of any other antimicrobial agent such patients will be clinically evaluated and appropriate laboratory tests, including cultures, will be performed to ensure that the information required to evaluate the discontinued study drug therapy will be available and recorded on the CRFs. Patients who receive at least one dose of the study drug will be evaluated for safety. Every effort will be made to follow-up such patients, including patients who are dropped from the study for any reason. Trained health workers will be sent to locate patients who fail to show up for the follow-up assessments at their homes. Parents will be encouraged to comply with the follow up visit.

Follow-up procedures for patients prematurely withdrawn from the study

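### The per-protocol definition keeps every failure with watery stool beyond 48 hours without saying which validity criteria still apply, so membership can depend on outcome

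*Protocol*

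**What the plan says.** Section 5.10.1 of the protocol, and the matching part of the protocol outline, define the PP set in two sentences. The first sets the entry rule: "Patients will be included in the PP analysis if they satisfy the criteria for a valid course". The second adds failures: "Patients regarded as treatment failures (continuation of watery stool for > 48 hours) will be included in the PP analysis".

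A valid course requires *V. cholerae* O1 or O139 isolated before treatment, no other systemic antimicrobial, compliance, no protocol violation that affects efficacy, and eligibility. Section 5.10.1 also requires test-of-cure data. Compliance is defined by regimen: "Documented adequate compliance with administration of the single ciprofloxacin dose, or at least 10 doses of the erythromycin medication". In addition: "Non-compliance will also be considered if two consecutive doses of the study medication are missed by a patient".

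Two criteria already carry their own exemption for failures. Other antimicrobials are allowed "unless it is done consequent to declaration of" clinical failure, and the data criterion reads: "Efficacy data from the test of cure visit is available, unless there has been an earlier treatment failure".

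Three other sections bear on the point:
- Section 5.9: on lack of efficacy, "the study drug will be stopped and such patients will be treated with an effective alternative drug".
- Section 5.4.1: a child who vomits within 30 minutes of dosing is not valid for efficacy.
- Section 5.8.1: a child given concomitant antimicrobials is a violator and not valid for efficacy. If the antimicrobial was started for the primary illness, the child counts as a treatment failure instead.

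**The concern.** The second PP sentence sets no condition. Taken literally, two children with the same defect, such as too few erythromycin doses before any failure or an eligibility breach, are handled differently according to how they fared. The one with watery stool beyond 48 hours is analysed and the one who recovered is dropped. A failure by recurrence, the other limb of clinical failure in Section 5.10.2, is not named in the sentence and must still have a valid course.

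When invalid failures are kept and invalid successes are dropped, the observed success rate falls. If the defect arises mainly in one arm, the comparison shifts. The 10-dose rule and the rule on two consecutive missed doses can exclude only children on the 12-dose regimen. The arm pushed down is therefore the comparator, and the -15 point margin becomes easier to meet.

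The trial is also open. If the sentence has to be interpreted when the analysis sets are formed, that choice could be made with treatment and outcome known.

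**Working it through.** **The plan's own figure.** Section 9.1 gives 80 per group (0.85 v 0.80, margin 0.15, two-sided 5%, power 90%, Farrington-Manning). The restricted estimates at the margin are 0.7216 and 0.8716, so

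n = [1.960·√(0.7216·0.2784 + 0.8716·0.1284) + 1.2816·√(0.85·0.15 + 0.80·0.20)]² / 0.20² = 79.5, or 80.

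Also 160/0.9 = 178, in line with 180. The sample size is sound and this point does not affect it.

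**Does the failure sentence override any criterion?** Erythromycin is given every 6 hours. Doses at hours 0 to 42 make 8, the dose at hour 48 is the ninth, and the tenth falls at hour 54. A failure whose drug is stopped at 48 hours has had 8 or 9 doses and cannot meet the 10-dose rule. Neither exemption inside the valid-course list covers doses, so this child enters PP only through the second sentence. The sentence therefore overrides at least one criterion, and the text does not say whether it overrides others.

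**Effect on the erythromycin rate.** Let p be the true success rate and q the share of children who break a validity rule regardless of outcome. With invalid successes dropped and all invalid failures kept:

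- apparent rate r = p(1−q) / [p(1−q) + (1−p)]
- children retained = n[p(1−q) + (1−p)]

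For p = 0.80 and q = 0.10: r = 0.72/0.92 = 0.783, and 90 × 0.92 = 82.8 children retained.

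**Effect on the error rate.** Set the true rates on the margin (0.65 v 0.80), with 90 per arm and invalidity in erythromycin only. Then

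P(lower bound ≥ −0.15) = Φ[(0.65 − r + 0.15)/SE − 1.960], with SE² = 0.65·0.35/90 + r(1−r)/retained.

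For q = 0.10: SE = 0.0677, and Φ(0.0174/0.0677 − 1.960) = Φ(−1.703) = 4.4%. The last column is from 400,000 simulated trials per row.

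| q, erythromycin only (assumed) | r | Error, formula | Error, simulated |
|---|---|---|---|
| 0 | 0.800 | 2.5% | 2.6% |
| 2% | 0.797 | 2.8% | 2.9% |
| 3% | 0.795 | 3.0% | 3.0% |
| 5% | 0.792 | 3.3% | 3.3% |
| 10% | 0.783 | 4.4% | 4.5% |

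**Two variations at q = 10%.**
- If half of failures are recurrences (assumed) and get no exemption, r = 0.72/(0.72 + 0.10 + 0.09) = 0.791 and the error is 3.4%.
- If both arms have 10% invalid, ciprofloxacin falls to 0.585/0.935 = 0.626 and erythromycin to 0.783. The apparent difference is −0.157 and the error is 2.0%, below nominal.

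**Deleting the sentence.** If a share f of erythromycin failures were dropped for not reaching dose 10, the apparent rate would be 0.80/[0.80 + 0.20(1−f)]. That is 0.842 at f = 25% and 0.889 at f = 50%, a larger distortion in the other direction.

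**The case against.** The best defence is that the sentence is a safeguard. A failure stopped at 48 hours cannot take 10 erythromycin doses, so without such a sentence these failures would vanish from PP and flatter the comparator. The list also writes out two exemptions for failures, which would be redundant if failures skipped the whole list. The sentence can therefore be read as a reminder not to discard failures, with the other criteria intact. This stands as a plausible reading and as a reason to keep failures in. It does not settle the text, because the sentence must lift the dose rule and does not say where it stops.

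Sections 5.4.1 and 5.8.1 separately make early vomiters and most children given other antimicrobials invalid for efficacy, and Section 5.9 stops the drug when both admission cultures are negative. This narrows the practical opening largely to missed doses and ineligibility. It also means that the literal PP sentence conflicts with 5.4.1 and 5.8.1.

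On size, Section 5.7 has study nurses give the doses on the ward, so non-compliance may be small. Only the missed-dose criteria are specific to one arm. Section 9.4 applies the margin without naming an analysis set. All of this stands.

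A reader might infer two stronger claims:
- **That the ITT set has the same fault.** Its second sentence is similar: "Patients regarded as treatment failures, as discussed above, will be included in the ITT analysis". But ITT requires only diagnosed cholera and one dose, with no compliance or valid-course test, so failures bypass no such test there. Any doubt about the diagnosis is not specific to one arm.
- **That 10% invalidity in erythromycin alone is the plan's own rate.** The plan's 10% covers all causes and is split evenly, 90 to 80 in each arm. Nine of 90 in one arm and none in the other is 9/180 = 5% overall.

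**Conclusion.** The point holds for the PP set only. As written, PP membership can depend on outcome for children with watery stool beyond 48 hours, and the sentence conflicts with Sections 5.4.1 and 5.8.1.

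The direction is conditional. Missed-dose invalidity favours non-inferiority; defects equally common in both arms do not, and make the test slightly conservative at the margin.

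The size is modest: about 2.9% to 4.5% one-sided error against a nominal 2.5%, for an assumed 2% to 10% invalidity confined to erythromycin and unrelated to outcome, and less if some failures are recurrences. These shares are assumptions. The result matters only where the PP set is used to judge the margin. The correction is worth making because it is cheap and removes a decision that would otherwise be left open in an unblinded trial.

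**What to change.** Keep failures in the PP set. In Section 5.10.1 and the protocol outline, replace the second PP sentence with:

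*A treatment failure is exempt only from criteria that the failure itself makes impossible (doses not given after failure was declared, antimicrobials given because of it, later test-of-cure data). All other valid-course criteria, including compliance with doses due up to the failure, apply to failures and successes alike.*

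Reconcile this text with the efficacy exclusions in Sections 5.4.1 and 5.8.1, so that each child has one status whatever the outcome. The ITT definition needs no change on this account.

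The cost is one sentence in two places. A few invalid failures will leave the PP set. The sample size and study procedures do not change.

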5.10.2 Trial objectives

The aims of this study are to investigate the efficacy of a single dose of ciprofloxacin oral suspension in comparison to erythromycin oral suspension for treatment of severe cholera in children due to *V. cholerae* O1 or O139, and to evaluate the safety (particularly musculoskeletal safety) of the drug.

Criteria for Evaluation of Study Objectives

As measures of effectiveness, the primary and secondary outcome measures will be compared.

Primary outcome measures

- Rates of clinical success at test of cure visit.

Secondary outcome measures

- Rates of bacteriologic success at test of cure visit.
- Duration of diarrhoea.
- Rates of clinical relapse.
- Rates of bacteriological relapse.
- Duration of faecal excretion of *V. cholerae* O1 or *V. cholerae* O139.
- Measurements of six-hourly volume of watery stool will be done for the period in which patients are hospitalised.
- Proportion of patients requiring unscheduled intravenous fluids.
- Frequency of vomiting and its volume
- Frequency of stool per day.
- Frequency of vomit per day.
- Safety.

Ciprofloxacin concentrations will be determined for both stool and serum. Stool will be collected in six-hourly for the first 72 hour of the study (thus 12 stool samples per patient). Blood samples will be taken from each patient during one of four time periods; before drug administration; within 1 hour of first drug administration; 1-2 hours after first drug administration; and 4-12 hours after the first dose. A 1-ml sample will be required at each time window.

Definitions

Response to therapy will be evaluated at test of cure visit (Day 5).

Test of cure (End of Day 5)

The clinical response will be defined as:

- **Clinical success:** cessation of watery stool within 48 hours of administration of the study drug without recurrence by Day 5.
- **Clinical failure:** continuation of watery stool for > 48 hours, or initial cessation with recurrence on or before Day 5.

The bacteriological response will be defined as:

- **Bacteriological success:** eradication of the infecting *V. cholerae* organism from faecal specimens within 48 hours of initiation of the study drug without its subsequent isolation by Day 5.
- **Bacteriological failure:** isolation of infective *V. cholerae* O1 or O139 from a faecal sample on Days 3, 4 or 5.

5.10.3 Safety

All patients who receive at least one dose of the study drug will be evaluated for safety. All adverse reactions or unusual events must be described on the AE page of the CRF. This report must include a description of the adverse event including the time of onset, duration, whether or not the study treatment was discontinued, what corrective measures were taken, the outcome of the adverse event, and the relation to the study drug. Safety will also be evaluated through careful reporting of laboratory tests of renal, hepatic and haematological functions and serial examination of the joints performed before, during and after administration of the study drug.

6. Warning / precautions

General

Please refer respectively to the ciprofloxacin suspension and erythromycin package inserts for warnings/precautions presented in Appendix 12.6.

Hypersensitivity and known adverse drug reactions to the investigational products and/or the class of products

Fluoroquinolone antibiotics such as ciprofloxacin are generally well tolerated and very rarely associated with serious or life-threatening adverse reactions (i.e. reactions possibly or probably related to drug therapy). Indeed, most of the adverse reactions associated with ciprofloxacin are mild and only infrequently discontinuation of treatment (i.e. < 2% of patients) is required. The reported adverse effects include metabolic/nutritional disorders (elevation of serum creatinine, BUN, hepatic enzymes, LDH, alkaline phosphatase), digestive disorders (nausea, vomiting and diarrhoea); skin and skin appendages (rash mainly), musculoskeletal (articular pains, myalgia, tendinopathy) and CNS disorders (headache, convulsive seizures and dizziness). Additional adverse effects include punctuate skin haemorrhage, haemorrhage bullae, vasculitis, Steven's-Johnson's Syndrome, interstitial nephritis and hepatitis. Effects on blood and blood constituents can occur and the most commonly seen are eosinophilia, leukopenia, leukocytosis and anaemia. Further information is given in the Investigator's Brochure.

Precautions for use

As with other quinolones, ciprofloxacin should be used with caution in patients with known or suspected CNS disorders such as severe cerebral arteriosclerosis, epilepsy and other factors that predispose to seizures. Serious and occasional fatal hypersensitivity (anaphylactic) reactions, some following the first dose, have been reported in patients receiving quinolone therapy. Such serious events require immediate emergency treatment as clinically indicated. Severe hypersensitivity reactions characterised by rash, fever, eosinophilia, jaundice and hepatic necrosis with fatal outcome have also been reported extremely rarely in patients receiving ciprofloxacin along with other drugs. As the possibility that these reactions were related to ciprofloxacin cannot be excluded, the drug should be discontinued at the first appearance of a skin rash or any other sign of hypersensitivity. Pseudomembranous colitis has been reported with nearly all antibacterial agents including ciprofloxacin, and thus it will be important to consider this diagnosis in patients who present with diarrhoea subsequent to the administration of antibacterial agents. As with other broad-spectrum antimicrobial agents, prolonged use of ciprofloxacin may result in overgrowth of non-susceptible organisms. Repeated evaluation of the patient's condition and microbial susceptibility testing is essential. If superinfection occurs during therapy appropriate measures should be taken.

Drug interactions

As with other quinolones, concurrent administration of ciprofloxacin with theophylline may lead to elevated serum concentrations of theophylline and prolongation of its elimination half-life with increased risk of theophylline-related adverse reactions. If concomitant use cannot be avoided, serum levels of theophylline should be monitored and dosage adjustments made as appropriate. Some quinolones, including ciprofloxacin, may interfere with the metabolism of

caffeine leading to reduced clearance of caffeine and prolongation of its plasma half-life. Quinolones have been reported to enhance the effects of the oral anti-coagulant warfarin or its derivatives. When these products are administered concomitantly, prothrombin time or other suitable coagulation tests should be closely monitored. Some quinolones, including ciprofloxacin, have been associated with a transient rise in serum creatinine in patients receiving cyclosporine concomitantly. Probenecid interferes with renal tubular secretion of ciprofloxacin and increases its serum concentration. As alkalinisation of urine is associated with ciprofloxacin crystal formation, urine-alkalising agents should be avoided while receiving the drug. However, as children in Bangladesh rarely use the above-mentioned medicines, it is not planned to enrol any patient taking these medicines into this study.

Magnesium hydroxide or aluminium hydroxide-containing antacids may interfere with the absorption of oral ciprofloxacin resulting in reduced serum and urine concentration. Therefore, ciprofloxacin should be administered either 1-2 hours before, or at least 4 hours after administration of these preparations if their use can not be stopped. It is not anticipated that antacids will be administered to any child enrolled in this study.

Carcinogenesis, mutagenesis and impairment of fertility

Long term carcinogenicity studies in mice and rats have been performed. No carcinogenic or teratogenic effects of ciprofloxacin were noted in these species after daily oral administration of the drug for up to 2 years. Reproduction studies performed in mice, rats and rabbits using parenteral and oral administration did not reveal any evidence of teratogenicity, impairment of fertility, or impairment of peri-/post-natal development.

Overdose

If a dose greater than the prescribed study dose (20 mg/kg body weight of ciprofloxacin as a single dose, or 12.5 mg/kg individual dose of erythromycin) is inadvertently given to any patient, patients will be carefully observed. Observation will include monitoring of respiratory and cardiovascular functions, and appropriate treatment will be provided whenever indicated. Only a small amount of ciprofloxacin (< 10%) is removed from the body after haemodialysis or peritoneal dialysis. The entire history of the incident, and every action taken, should be carefully recorded. When appropriate, blood and urine samples should be obtained for determination of drug concentration. Such a situation will be considered a **Serious Adverse Event** and the appropriate documentation will have to be completed.

7. Ethical aspects and good clinical practice compliance

7.1 Good clinical practice

All clinical work conducted under this protocol is subject to Good Clinical Practice (GCP) rules, and this may include inspection by Bayer staff or representative, government authorities and/or Ethical Review Committee of ICDDR,B at any time. The investigator must agree to these inspections. The investigator must adhere to the above principles in addition to any applicable local regulations.

7.2 Informed consent and subject information

Informed Consent must be obtained from parents/guardians of each of the participating children in the study after of the aims, methods, anticipated benefits and potential hazards of the study has been explained to them. The investigator must also explain that the patients are completely free to refuse to enter the study or to withdraw from it at any time. This informed consent must be obtained in the presence of a witness and his/her signature together with the date must be obtained. If possible, assent must be obtained from the child.

Informed consent

Parents or guardians must provide informed consent for participation of their children in the study before enrolment. The investigators will explain the purpose and procedures of the study, tests to be administered, potential or possible hazards, and that patients may be withdrawn from the study at any time without compromising their treatment. Parents of patients to be included in the pharmacokinetic subset will have to give consent to this procedure specifically.

If it is not possible to obtain written consent because of the inability of the parents or guardians to read or write, they may indicate their consent by putting their thumb impression on the consent form, provided this is done after explaining the purpose and procedures of the study. Consent must be obtained in presence of a witness who will also put his/her signature on the consent form. A copy of the signed consent form will be given to the parents or guardians. The date of obtaining informed consent will be documented on the patient's hospital records.

Instructions to the parents/guardians

As children will be hospitalised, no specific instructions for drug ingestion will be provided. However, if discharged from the hospital before the end of the study, parents or guardians will be urged to bring back their children to the hospital for further assessments as outlined in this protocol. Parents or legal guardian will be instructed to report any unexpected adverse events or changes to the investigators immediately upon their occurrence. They will be cautioned that antacids must not be administered together with the study drug, and that in the event of a need antacids may be given 1-2 hours before or at least 4 hours after administration of the study drug. However, the use of antacids in this study is not anticipated.

